## Sample Size Calculation

**Table 2: Sample Size Calculations**  
(40 providers/clusters, ICC = 0.02, power = 0.8)

Screening Orders (Control Group)	Screening Orders (Experimental/Intervention Group)	Sample Size (Total)
50%	30%	240
	35%	440
	38%	760
	40%	200
	25%	400
	28%	680

Preliminary data demonstrate that approximately 1,200 screen-due Veterans between 70-75 years of age with comorbid illness will present to the VA Ann Arbor Medical Center and the Toledo CBOC over a 24-month period. Assuming a 50% participation rate (based on the participation rate observed in co-investigator [name]'s ongoing VA-funded CRC screening decision aid trial, which uses a similar recruitment method), we will have the capability of enrolling 600 patients over this time period. Preliminary data show that 35% of these individuals will complete a screening test within 6 months of the clinic visit. Based on this value and prior data on screening completion rates, we estimate that a screening test is ordered at approximately 50% of visits among patients who receive usual care (control event rate (CER) = 50%). Our survey data (see Preliminary Data, B.5.c) suggest that the VC intervention will reduce the CER by at least 30%, yielding an estimated experimental event rate (EER) of 35%. Study sites employ over 50 primary care providers (clusters), and we

expect that approximately 75% of these providers will choose to participate (based on an ongoing CRC screening study involving primary care providers at VAAAHS). Finally, based on preliminary data, we assumed an ICC of screening orders within provider of 0.02. Under these assumptions, a sample size of 440 patients would provide 80% power to detect a meaningful reduction in screening orders (H1a) (Table 4). Thus, with the proposed sample size of 600 patients, we will have more than 80% power to detect a meaningful difference in screening orders (H1a) between control and experimental groups (using two-tailed tests at an alpha of 0.05). We anticipate that this sample size will also be adequate to detect a difference in benefit-concordance of screening orders between study arms (H1b), since this analysis will simply require the addition of two additional terms in our regression equation.

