**Most recent IRB continuation approval: 10/30/2018**

# PROTOCOL AND STATISTICAL ANALYSIS PLAN

## Specific Aim and Hypotheses

To evaluate the impact of a 3-part decision aid (DA) intervention of an individualized decision-aid (1), provider education (2), and modified performance measure/reminder (3) versus a pragmatic control (PC) that includes provider education and modified performance measure/reminder, but no decision aid, on the frequency of CRC screening orders in a cluster-randomized controlled trial.

*H1a: Individuals in the DA group will receive screening orders less often than those in the PC group.*

*H1b: Individuals in the DA group will receive screening orders that are more concordant with screening benefit than those in the PC group.*

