## Research Design and Methods

The 30-month, 3-part intervention is directed at patient-, provider-, and system-level factors. First, we provided patients with a personalized decision aid (intervention component 1 of 3) that worked to educate Veterans about the underlying reasons for screening and informed them about the risks and benefits (tailored to demographic characteristics and comorbidity burden), thereby enhancing their conceptual understanding and increasing the accuracy of their perceptions about CRC and screening. The decision aid also included a values-clarification exercise to help them clarify their personal values and preferences regarding screening. Second, we educated providers (intervention component 2 of 3) to increase their general knowledge of the underlying data on screening in elderly individuals. Individualized risk information from the decision aid was also available to providers, enhancing their knowledge of the risks and benefits of screening specific to their patients. Finally, we addressed system-level factors by modifying performance measurement and clinical reminder (performance management) systems to ease institutional pressures on providers to order screening without discussing risks and benefits (intervention component 3 of 3).

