## Research Specifications

**Table 1: Design of Pragmatic Cluster-Randomized Trial**

Design	Cluster-randomized controlled trial (RCT) 1:1 provider (Full Time Equivalent or FTE) randomization
Setting	VA Ann Arbor Medical Center and its largest CBOC (Toledo), both of which are under the jurisdiction of VAAAHS leadership and a single IRB.
Study Population	
Veterans aged 70-75 who meet the following criteria:
 
 
1) Average risk for CRC
 
2) Due for screening according to the 2008 USPSTF CRC screening guideline
 
3) No documentation of limited life expectancy
 

Veteran-Centered Intervention (VC) (3 components)	
 
1) CRC screening decision aid
 
2) Provider training and education
 
3) Modified CRC screening performance management system 
 
a. Modified clinical reminder
 
b. Modified performance measure
 
c. Modified provider feedback and performance pay
 
 
 

Pragmatic Control (PC) (3 components)	
 
1) No CRC screening decision aid
 
2) Provider training and education
 
3) Modified CRC screening performance management system 
 
a. Modified clinical reminder
 
b. Modified performance measure
 
c. Modified provider feedback and performance pay
 
 
 

Outcomes	
 
1) Proportion of primary care clinic visits where CRC screening is ordered (H1a)
 
2) Benefit-concordance of screening orders (H1b)
 
3) Screening tests completed (utilization) (H1c)
 

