## Primary Outcome Measure

**CRC screening orders (H1a):** We hypothesized that Veterans randomized to the DA intervention would receive fewer screening orders than those randomized to the pragmatic control (H1a). Thus, the primary dependent variable in our analysis was whether screening was ordered at the clinic visit (dichotomous; gave 2 weeks for the order to appear in patients’ medical records)). We then determined whether screening was ordered through manual record review.

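### The power stated for H1a is calculated for usual care against the full three-part package, not for the randomised DA-versus-PC comparison

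*Combined protocol and SAP*

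**What the plan says.** The Specific Aim compares the three-part DA intervention "versus a pragmatic control (PC) that includes provider education and modified performance measure/reminder, but no decision aid". The Primary Outcome Measure section states H1a for the same pair of arms: "Veterans randomized to the DA intervention would receive fewer screening orders than those randomized to the pragmatic control (H1a". Table 1 lists provider training and all three performance-management items under both arms, down to "Modified provider feedback and performance pay". The only listed difference is the decision aid.

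The Sample Size Calculation uses other inputs. The control rate is defined by "a screening test is ordered at approximately 50% of visits among patients who receive usual care (control event rate (CER) = 50" per cent. Survey data then "suggest that the VC intervention will reduce the CER by at least 30%, yielding an estimated experimental event rate (EER) of 35" per cent. VC is Table 1's name for the arm with all three components.

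Power is attached to H1a by name in two places: "a sample size of 440 patients would provide 80% power to detect a meaningful reduction in screening orders (H1a", and "with the proposed sample size of 600 patients, we will have more than 80% power to detect a meaningful difference in screening orders (H1a".

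**The concern.** The control rate describes patients who receive none of the study components, and the reduction is attributed to an arm that receives all of them. The trial randomises neither of those contrasts. It compares all three components with two of the three, so the effect that matters for H1a is what the decision aid adds.

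The shared components may themselves lower ordering. Research Design and Methods says the performance-management change is meant "to ease institutional pressures on providers to order screening without discussing risks and benefits". A change with that purpose could bring the PC rate below 50%. The plan gives no size for this effect or for provider education, and it does not say that PC is expected to order at the usual-care rate.

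The consequence is mainly interpretive. A reader who accepts more than 80% power at face value could take a null DA-versus-PC result as good evidence that the decision aid does nothing, when the study may have had much less power for that comparison. The randomised comparison and the mixed model in Data Analysis are unaffected.

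**Working it through.** **Inputs from the plan.** 40 providers, ICC 0.02, two-sided alpha 0.05, 80% power, 1:1 allocation, 50% versus 35%, totals of 440 and 600. **My assumptions:** every other PC or DA rate below.

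**1. Reproduce the plan's figure.** Patients per arm before clustering, with p̄ the mean of the two rates and d their difference:

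n = [1.96·√(2p̄(1−p̄)) + 0.842·√(p1(1−p1) + p2(1−p2))]² / d²

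For 50% versus 35% (p̄ = 0.425, d = 0.15), n = 169.3. The Fleiss continuity correction, n/4·[1 + √(1 + 4/(nd))]², gives 182.4.

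The design effect is 1 + (N/40 − 1)·0.02. Solving for the total gives N = 2n·0.98 / (1 − 2n·0.02/40):
- without correction: 338.6·0.98 / (1 − 0.1693) = 400
- with correction: 364.8·0.98 / (1 − 0.1824) = 437, against 440 in the plan.

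The plan's arithmetic is sound. The question is which comparison its inputs describe.

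**2. Power at a given total.** Effective patients per arm: m = (N/2) / design effect. At 440 the design effect is 1.20 and m = 183.3. At 600 it is 1.28 and m = 234.4.

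Power = Φ{[d·√m − 1.96·√(2p̄(1−p̄))] / √(p1(1−p1) + p2(1−p2))}

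With continuity correction, m is replaced by m·[1 − 1/(md)]².

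- 50% versus 35% at 600: (2.296 − 1.370)/0.691 = 1.340, power 91.0% (89.4% with correction).
- 45% versus 35% at 600: (1.531 − 1.358)/0.689 = 0.251, power 59.9% (56.2% with correction).

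**3. Vary the PC rate at N = 600** (power without / with correction):

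| PC rate | DA fixed at 35% | Decision aid alone cuts orders by 30% (relative) |
|---|---|---|
| 50% | 91.0 / 89.4% | 91.0 / 89.4% |
| 48% | 81.7 / 79.1% | 89.0 / 87.1% |
| 45% | 59.9 / 56.2% | 85.5 / 83.2% |
| 43% | 42.7 / 39.0% | 82.9 / 80.3% |
| 40% | 20.0 / 17.4% | 78.5 / 75.5% |

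If half of the 15-point fall came from the shared components (PC 42.5%, DA 35%), power would be 38 / 35% at 600 and 31 / 28% at 440.

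**4. Lowest PC rate that keeps 80% power** (without / with correction):

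| Total | DA fixed at 35% | 30% relative cut |
|---|---|---|
| 600 | 47.7 / 48.1% | 41.0 / 42.8% |
| 440 | 49.4 / 50.0% | 47.7 / 49.8% |

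At 600 the PC rate can fall about 2 points below 50% in the first case and about 7 to 9 in the second. At 440 the slack is 0 to about 2 points.

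**5. Smallest difference detectable with 80% power** (without / with correction):
- N = 600: 12.8 / 13.2 points from PC 50%; 12.2 / 12.6 from PC 40%.
- N = 440: 14.4 / 15.0 points from PC 50%; 13.7 / 14.2 from PC 40%.

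**The case against.** **No loss of power is shown.** Both quantities that would settle it, the PC rate and the decision aid's own effect, are missing, and every low figure above uses an assumed PC rate. This stands. The conclusion is that 80% power is not demonstrated for H1a, not that the trial is underpowered.

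**VC may be only an arm label.** The 30% reduction could mean the experimental arm against the trial's own control, and the survey behind it (Preliminary Data, B.5.c) is not in the documents. It might concern the decision aid alone. This cannot be checked. Even so, the 30% is applied to a rate defined for usual care, so the PC baseline remains unsupported.

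**Table 2 already includes a lower control rate.** Its last three rows are damaged in the text but fit a 40% control with 20%, 25% and 28%: I obtain 196, 387 and 688 against the printed 200, 400 and 680. By contrast, 50% versus 40% would need 1,346, so the printed 200 beside 40% cannot be that comparison. The table therefore varies the control rate in part. It keeps differences of 12 to 20 points, though, and the text does not connect these rows to PC. If the shared components account for part of the 15 points, the remaining difference could lie below the table's range.

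**Fixing DA at 35% is harsh.** The plan expects a reduction of at least 30%, so DA could be lower; PC 45% with DA 30% has 92 / 91% power at 600. This is fair, and it is why both scenarios should be shown.

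**Conclusion.** The concern holds. The figures of 80% power at 440 and more than 80% at 600 are correct for 50% versus 35%, but the plan ties those rates to usual care and to the full package. They carry over to H1a only if provider education and the modified performance management leave ordering almost unchanged, or if the decision aid alone has a large enough effect. The plan argues neither.

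The size of any loss cannot be fixed from the documents. With PC between 50% and 40%, power at 600 runs from 91% down to 20% if DA stays at 35%, and from 91% down to 78% if the decision aid alone gives a 30% relative reduction (without continuity correction). What can be stated without knowing the effect is the limit of detection: about 13 points at 600 and about 14 to 15 points at 440, given 40 providers and an ICC of 0.02.

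**What to change.** In the Sample Size Calculation:
- Replace the usual-care control rate and the VC experimental rate with an assumed PC order rate and an assumed DA order rate, each with its basis. If PC is taken to equal usual care, say so and justify it. As much of the plan is written in the past tense, a dated clarifying note that leaves the original justification visible would serve as well.
- Add a short table of DA-versus-PC power for PC rates of 40% to 50% under two labelled assumptions: DA fixed at 35%, and a 30% relative reduction by the decision aid alone.
- State the smallest DA-versus-PC difference detectable with 80% power at 600 (about 13 points). Qualify the two power sentences: the claim at 440 holds for differences of about 14 to 15 points, the claim at 600 for about 13.

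In Data Analysis, commit to reporting the DA-minus-PC difference in order rates with its 95% CI, so that a null result is read against that limit. The planned logit mixed model does not give this directly; a marginal estimate derived from it is enough.

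The cost is wording, a small table and one derived estimate, and the stated power becomes less favourable. No extra patients are needed, and the randomisation and the primary model stay as they are.
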